Official title of study:

A Personalized Approach to Effects of Affective Bias Modification on Symptom Change and Rumination

NCT04137367

Date: September 23rd 2019

1. *A personalized approach to effects of affective bias modification on symptom change and rumination. A randomized controlled trial.*

2. Introduction.

A main objective of this project is to investigate whether transdiagnostic rumination mediates the effects of affective bias modification on depressive symptoms. By combining general mechanisms research with a personalized symptom network approach, we will be in the forefront of understanding how a drug-free treatment option works and for whom it works best.

There is a growing consensus that the traditional approach to mental disorders in psychopathology research is constraining new scientific discoveries. Up until recently, research has been guided by the idea that a specific constellation of psychiatric symptoms reflects a specific psychiatric disorder, and that a specific pathogenic pathway causes this. However, findings based on this approach have not aligned with findings from clinical neuroscience and genetics, is poor in predicting treatment response, and does not seem to capture the underlying mechanisms of dysfunction (Insel et al., 2010). The problem is particularly disturbing for depression research, as depression is a very heterogenic disorder (Goldberg, 2011) with numerous plausible etiological and maintaining pathways (Charney & Manji, 2004; Wittenborn, Rahmandad, Rick, & Hosseinichimeh, 2016) and high levels of comorbidity (e.g., anxiety and alcohol use disorder; (Brown, Campbell, Lehman, Grisham, & Mancill, 2001; Kessler et al., 1997).

Rumination. There is growing evidence that rumination, a maladaptive form of self-reflection, might constitute a transdiagnostic factor. A particularly maladaptive sub-type of rumination, brooding, reflects the degree to which individuals passively focus on symptoms of distress and the meaning of those symptoms. Brooding is a vulnerability factor to Major Depressive Disorder (MDD) and it contributes to the development and maintenance of the disorder (Abela & Hankin, 2011; Sarin, Abela, & Auerbach, 2005). In bipolar disorder (BP), compared to MDD, ruminative responses are even more present (Kim, Yu, Lee, & Kim, 2012). Rumination predicts prospective changes in anxiety (Segerstrøm, Stanton, Alden, & Shortridge, 2003), as well as alcohol use in outpatients with a diagnosis of alcohol abuse, independent of depression and initial level of alcohol use (Caselli et al., 2010). Furthermore, brooding mediates the prospective relation between anxiety and depression (Grant et al., 2013). These associations suggest that rumination may play an important role across psychopathologies and contribute to the high rates of comorbidity among those disorders (Caselli et al., 2010; McLaughlin & Nolen-Hoeksema, 2011).

Affective bias. Affective biases, i.e. preferential attention to threatening information have been documented in subjects with clinical and subclinical levels of anxiety (Bar-Haim, Lamy, Pergamin, Bakermans-Kranenburg, & Van IJzendoorn, 2007; Cisler & Koster, 2010). It has also been demonstrated that clinically depressed subjects, previously depressed subjects and never-depressed individuals at high risk because of family history, all display a bias towards sad faces (Gotlib, Krasnoperova, Yue, & Joormann, 2004; Joormann & Gotlib, 2007; Joormann, Talbot, & Gotlib, 2007). Studies indicate that the negative affective biases may constitute causative, vulnerability and maintenance factors for affective disorders, like depression and anxiety (Chan, Goodwin, & Harmer, 2007; MacLeod, Rutherford, Campbell, Ebsworthy, & Holker, 2002). However, although there have been quite a high number of studies examining affective biases in depression or anxiety individually, surprisingly few studies have examined affective biases among individuals with comorbid depression and anxiety (Gibb, McGahey, & Beevers, 2016).

Linking rumination, attentional control, symptoms and affective bias. Self-reports of rumination predict an affective bias towards negative stimuli, even when depressive symptoms are statistically controlled for (Donaldson, Lam, & Mathews, 2007). Negative biases are particularly strong in subjects with heightened disposition to engage in ruminative brooding (Joormann, 2006).

Rumination can be understood as dysregulated attentional focus on depression symptoms. Both trait and experimentally induced state rumination have been linked to impairment in executive control functions, in particular cognitive inhibition and switching (Joormann & Gotlib, 2010). This indicates that information-processing impairments might make it difficult for ruminators to disengage from negative content (Koster, De Lissnyder, Derakshan, & De Raedt, 2011).

The aforementioned findings have motivated an increase in interest in using knowledge about the mechanisms underlying the vulnerability and maintenance of affective disorders for therapeutic purposes (Harmer, Duman, & Cowen, 2017; Koster & Hoorelbeke, 2015). Given that one of the central mechanism in affective disorders is a selective attentional focus towards disorder-relevant stimuli, then reducing this focus could potentially alleviate the disorder. Computerized tasks that aim to induce changes to the bias in question have been developed (Hertel & Mathews, 2011). These procedures appear successful in reducing affective biases observed in depression, and might also lead to reductions in depression symptoms (Hallion & Ruscio, 2011).

The symptom network approach. Given the above challenges, there has been a call for multi-level etiological models involving multiple causal processes at the micro and macro level, within and outside the individual (Kendler, Zachar, & Craver, 2011). The network approach offers a promising conceptual framework to explore the complex interplay between important psychopathological processes at the dimensional level (Hofmann, Curtiss, & McNally, 2016). By network analysis one can determine which symptoms are the most central (i.e., influential) based on the amount of influence that flows from one symptom to another (Borgatti, 2005). See figure 2. Networks with many strong connections between symptoms (dense networks) are more likely pathogenic than networks characterized by weaker connections (Borsboom, 2017). Simulation studies show that in dense networks, only a minimal of worsening in a central symptom may trigger a downstream cascade of symptoms. This might lead to a “vicious cycle” of negative cognition and symptoms (Wichers, 2014), with a depressed state as the result (Cramer et al., 2016).

Using intensive time series data on symptoms in combination with cutting-edge statistics, such as graphical vector autoregressive modelling, we can capture the within- and between-person temporal dynamics of individual symptom networks (Wild et al., 2010). Relevant psychological, physiological and behavioral variables can be gathered relatively easily by the use of smartphones (Miller, 2012). Analyzing such time-series data can reveal dynamic processes within each individual (Trull & Ebner-Priemer, 2009). In this manner, symptoms and other variables can be tracked over time to optimally model the continuous dynamics of the interplay between processes during improvement and worsening of a disorder, and before and after interventions. This approach can provide a more fine-grained examination of the dynamic interplay between depression-related processes at the individual level, and possibly help identify symptom profiles for which ABM might be effective. Thus, the network approach provides a potential framework for personalized assessment and treatment (Fried et al., 2017), and guide clinicians in choosing treatments that are tailor-made to address each patient’s problem more effectively (Fisher, Reeves, Lawyer, Medaglia, & Rubel, 2017).

Recently, researchers have advocated for the inclusion of non-symptom variables that are assumed to be plausible causal candidates in the etiology or maintenance of disorders (Jones, Heeren, & McNally, 2017). Rumination and affective bias are relevant variables that can be included in network analyses of depression. To date, only a few studies have included such variables (Heeren &

[figure not shown]

Figure 1. The relation between depression, attentional control, affective bias and rumination. Adapted from LeMoult & Gotlib (2018).

[figure not shown]

Figure 2. Example of a depression symptom network

McNally, 2016; Hoorelbeke, Marchetti, De Schryver, & Koster, 2016). Whether rumination mediates the relation between affective bias and depressive symptoms is still not accounted for. For whom, and under which circumstances these interventions have reliable effects on depression symptoms is also under debate (Cristea, Kok, & Cuijpers, 2017; Grafton et al., 2017). The intervention of this clinical trial is a computerized training program, called affective bias modification (ABM), known to produce a generalized affective bias change (Browning, Holmes, Charles, Cowen, & Harmer, 2012). A main aim of this project is to investigate how the effects of this ABM intervention on depressive symptoms are mediated by transdiagnostic rumination and how characteristics of the symptom network moderate these effects.

2.1. Needs description. Depression affects more than 300 million people worldwide and is an increasing global health issue (Bender & Farvolden, 2008), however, treatment efficacy is still unsatisfying (Cuijpers, van Straten, Bohlmeijer, Hollon, & Andersson, 2010). Forty percent of patients do not, or only partially, respond to treatment and less than one-third are completely recovered after treatment (Andrews, Issakidis, Sanderson, Corry, & Lapsley, 2004). Furthermore, MDD with co-morbid anxiety predicts poor outcome with a higher percentage of treatment resistance than either disorder occurring alone (Coplan, Aaronson, Panthangi, & Kim, 2015), requiring new treatment options. While all available treatments of depression, psychologically as well as pharmacological, seem to be about equally effective, little is known about who benefits from which treatment (Cuijpers & Christensen, 2017). By combining an intervention based on transdiagnostic neuroscientific knowledge with *Ecological momentary assessment (EMA) of affective symptoms*, this study might contribute to close this knowledge gap.

Whether ABM directly changes rumination in transdiagnostic clinical patients and has not been systematically investigated previously. If successful, ABM could improve the outcome for patients where negative affective bias is central, for example as a supplement to treatment-as-usual. If effective, ABM expands the possibilities to choose non-pharmacological treatment options, which is important to many patients. The ABM intervention is highly scalable and is an economic way to alleviate symptoms, and can be done in the patients homes (Holmes et al., 2018). Combining EMA and personalized statistical approaches may provide a low-cost assessment method aiding clinicians in identifying the processes that are most likely maintaining symptoms. This assessment method can easily be modified to capture other relevant pathological dynamics (e.g., resilience, relational problems, other symptoms). Identifying these processes more precisely, will have the potential to make interventions more focused on the patient's problem, and lead to better treatment efficacy.

3. Hypotheses, aims and objectives.

Primary hypothesis: Subjects who are in the active ABM group will exhibit less tendency for stress related (state) rumination compared to those in the placebo group (2 weeks). Active vs placebo ABM will decrease depressive symptoms (6 months) and this effect will be mediated by the change in state rumination. Densely connected symptom network and high strength centrality of rumination at baseline will moderate the effect of ABM. See figure 3.

[figure not shown]

Figure 3. Model of the primary hypothesis

Secondary hypotheses: After the intervention, patients with changes in affective bias after ABM develop a less densely connected symptom network and have reduced strength centrality of rumination. Reduced network density and reduced strength centrality of rumination after ABM leads to reduction in depressive symptoms at 6 months.

4. Project methodology

Design and participants. The Affective Bias Modification Task (ABM) will be applied in a randomized controlled, double blind clinical trial with 6 months follow-up. Personalized networks

are generated from prospective assessment of depression-related processes at baseline and follow-ups, allowing us to investigate for whom this procedure is effective. Patients (N = 150) will be recruited from an out-patient clinic at Diakonhjemmet Hospital, and randomized into one of three conditions: active, sham and assessment only. Patients aged 18-65 with depression (major depressive disorder) or bipolar disorder 2, with or without comorbid anxiety and/or alcohol use disorder will be included. Exclusion criteria are a history of mania, psychosis, or a neurological disorder.

4.1. Project arrangements, method selection and analyses.

Negative affective bias. In the dot-probe task (MacLeod et al., 2002) paired stimuli (e.g. a negative and a positive face) are presented, followed by one or two probes (dots) appearing in the spatial location of one of the stimuli. See figure 4. Participants are then required to press one of two buttons as quickly as possible to indicate the number of dots in the probe. Thus, if the participant systematically orients towards a negative emotional stimulus (i.e. has a negative affective bias), they respond faster to probes presented at the spatial location of the negative stimulus compared to probes at the location of the positive stimulus. Stimuli

presentation time is 50% 500 ms and 50 % 1000 ms (evenly distributed throughout the task). In total, the dot probe task will comprise 90 trials of paired images of faces of different valences.

The Facial Expression Recognition Task (FERT; (Harmer, O'Sullivan, et al., 2009) is another measure of negative affective bias and is included to make sure that biases measured with the dot probe task transfers to an independent measure. In this task, pictures of faces are gradually morphed between neutral, and positive and negative facial expressions. The detection threshold for correctly identifying the facial expression is the variable of interest.

Affective bias modification. The task is almost identical to the dot probe task. The differences are that the probe appears at the location of the most positive stimuli of each pair in 87 % of trials (encouraging a positive affective bias). In the control condition, there is no contingency between facial expressions shown and the probe location. Participants will do ABM in their homes (approx. 5 min.) twice a day for two weeks (28 sessions) using laptop computers provided by us. Our experience with previous ABM studies indicate good adherence by participants using this regime.

EMA of affective symptoms. The estimation of the each participant's symptom network is based on data from three separate two-weeks of EMA (baseline, follow-up and six months), conducted by means of the PsyMate™-app on their smartphones. The app pings four times per day (in the morning, middle of the day, afternoon, evening), at slightly irregular intervals, and instructs the participant to report on mood and symptoms guided by Positive and Negative Affective Schedule (PANAS; (Thompson, 2007)) and DSM-5 criteria of MDD, respectively, and the extent they have been engaged in brooding rumination. In total, the participant is pinged 56 times per two-week period and each self-report takes approximately 1 minute to complete.

Clinical and cognitive assessment. Diagnostic assessment will be made in accordance with the MINI International Neuropsychiatric Interview PLUS 5.0.0 (Sheehan et al., 2006). Depression symptoms will be assessed using Beck Depression Inventory – II (BDI-II; (Beck, Steer, & Brown, 1996)). Anxiety symptoms will be assessed using the Beck Anxiety Inventory (BAI; (Beck, Epstein, Brown, & Steer, 1988)). Trait rumination will be assessed by means of the Rumination Response Scale (RRS; (Treynor, Gonzalez, & Nolen-Hoeksema, 2003)). State rumination will be assessed by means of the Brief State Rumination Inventory (BSRI; Marchetti, Mor, Chiorri, & Koster, 2018)). General attentional control will be assessed by the Attention Network Test (ANT; Fan, McCandliss, Fossella, Flombaum, & Posner, 2005)).

[figure not shown]

Figure 4. Dot probe

[figure not shown]

Figure 5. Design, procedures and schedule. ABM = Attention Bias Modification. AUDIT = Alcohol use disorder identification test. BAI = Beck Anxiety Inventory. BDI-II = Beck Depression Inventory - Second Edition. DUDIT = Drug use disorder identification test. EMA = Ecological Momentary Assessment. FERT= Facial expression recognition task. MINI = MINI International Neuropsychiatric Interview PLUS 5.0.0. RSS = Ruminative response scale.

Negative mood induction paradigm. Drawing on diathesis-stress models of affective disorder (Disner, Beevers, Haigh, & Beck, 2011), we will include a negative mood-induction procedure prior to assessment of state rumination and stress reactivity (Westermann, Stahl, & Hesse, 1996). A standardized mood induction script, personalized by stressful autobiographical events (Sinha & Tuit, 2012), will be recorded for each patient. Upon listening to the script, they are asked to imagine themselves being in the situation. Imagery vividness scale (Sinha & Tuit, 2012) is used to assess how clear they manage to imagine themselves in the situation. Afterwards, subjects will be left alone for five minutes to trigger state rumination. A shortened version of the Profile of Mood States (POMS; 37 items) will be administered before and after the mood induction as a manipulation check (Shacham, 1983). Our research group have previously shown that POMS reflects changes in mood states over short intervals in healthy controls (Walderhaug et al., 2007). Stress reactivity is operationalized as reduced HRV (measured via the Polar RS800 heart rate monitoring system) and rising cortisol levels (measured via Salivette® saliva sampling). A meta-analysis of cortisol response after stress induction has shown that peak cortisol is reached 38 minutes after stress induction onset (Goodman, Janson, & Wolf, 2017). Between post-induction and recovery, the participants will be encouraged to watch emotionally neutral videos (selected National Geographic films). See figure 6 for procedure and time schedule.

[figure not shown]

Figure 6. Negative mood induction procedure. BSRI = Brief state ruminative inventory. HRV = Heart rate variability. POMS = Profile of mood states.

Statistical power. Calculation of statistical strength regarding detecting an effect of ABM is based on an assumption that 20 % in the placebo group will report 3 points improvement on BDI-II at follow-up compared to 50 % in the active ABM group. The National Institute for Health and Care Excellence (NICE, 2009) , suggests a difference of ≥ 3 BDI-II points is a clinically significant treatment effect for depression. By assuming 15 % drop-out at follow-up, 50 patients in each condition (total n= 100) will be required when $1 - \beta = .80$ and $\alpha = .05$. The literature provides no clear guidelines as to how many data points that is necessary to reliably estimate a patient's

symptom network, but simulation studies suggest adequate performance for estimating an eight-node network using 50 observations (Epskamp et al., 2018). Given multiple regression analysis with up to six predictors and a small effect size ($<.10$), $\beta = .80$ and $\alpha = .05$, the estimated required sample size is 81. When examining the effect of ABM, we are only interested in effect sizes of clinical relevance (i.e. < 0.25). Given an ANOVA repeated measures analysis with effect size = 0.25, $\beta = .80$ and $\alpha = .05$, the estimated required sample size to detect a difference in changes in the network metrics between the conditions is 34.

Mediation and moderation analysis. The mediation analysis, investigating whether the relation between ABM and symptoms change is mediated by rumination, will be performed according to the procedure established by Baron and Kenny (1986). The moderated mediation analysis, investigating whether ABM changes depressive symptoms as a function of symptom network, will be performed according to recommendations made by Muller, Judd, and Yzerbyt (2005).

Feasibility. Labs for conducting the research are available at the Department of psychology, University of Oslo. The biobank “Genes in cognition and Emotion” REK SørØst 2011/2593 will be used to store salvia samples. Twenty-five laptop computers for conducting the ABM-intervention and Polar watches for recording HRV are already acquired. Neurocognitive labs are available at the Department of Psychology. All questionnaires are translated into Norwegian by means of back translation procedures. The negative mood induction procedure will be piloted before commencement. The project is currently under evaluation by REK SørØst 2019/330. During the last decade, through our longstanding collaboration with Diakonhjemmet Hospital and other nearby clinics, we have managed to recruit hundreds of patients in different stages of their depressive illness to take part in clinical studies. The TSD (in Norwegian, Service for Sensitive Data) service will be used for storing and post-processing sensitive-data in compliance with the Norwegian “Personal Data Act” and “Health Research Act”. TSD is developed and maintained by USIT at the University of Oslo and supports research activities run at Norwegian public institutions.

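### The secondary network hypotheses rest on a group formed after randomisation and name no comparator, and the planned between-condition ANOVA of network metrics answers a different question

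*Combined protocol and SAP*

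**What the plan says.** Section 3 (Hypotheses, aims and objectives) gives two secondary hypotheses. The first is that "patients with changes in affective bias after ABM develop a less densely connected symptom network and have reduced strength centrality of rumination". The second is "Reduced network density and reduced strength centrality of rumination after ABM leads to reduction in depressive symptoms at 6 months". Neither names a control arm. The primary hypothesis just above them does: "Active vs placebo ABM will decrease depressive symptoms (6 months) and this effect will be mediated by the change in state rumination". Section 4 (Design and participants) randomises 150 patients to active, sham or assessment only.

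Section 4.1 supplies the measurements. Networks come from "three separate two-weeks of EMA (baseline, follow-up and six months". Affective bias is measured by the dot-probe task and by FERT, which "is included to make sure that biases measured with the dot probe task transfers to an independent measure". No change score or threshold says which patients count as having changed.

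One analysis of network change appears, in the Statistical power text: "Given an ANOVA repeated measures analysis with effect size = 0.25", for which the "required sample size to detect a difference in changes in the network metrics between the conditions is 34". The same text sizes a multiple regression with up to six predictors (81 patients) without naming an outcome, predictors or hypothesis. Under Mediation and moderation analysis, rumination is the mediator and the symptom network is the moderator. Section 3 places that moderator at baseline.

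**The concern.** Bias change is observed after randomisation, so patients who show it are not comparable by design with those who do not, or with the sham arm. Patients who improve for other reasons may change in bias, network and symptoms together. A test of the first hypothesis built on that group could then be positive although ABM did nothing to the network. The association would be real; reading it as an ABM effect would be wrong. The second hypothesis has the same weakness: nobody is randomised to network change, yet the wording is causal.

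At stake is the mechanistic claim. The active versus placebo contrasts in the primary hypothesis are not affected.

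**Working it through.** **1. Hypotheses against analyses (text available).**

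| Item | Uses bias change? | Uses network change? | Comparator or outcome named? |
|---|---|---|---|
| Secondary hypothesis 1 | Yes, to form the group | Yes, as outcome | No comparator |
| Secondary hypothesis 2 | No | Yes, as cause | Outcome yes, comparator no |
| Repeated measures ANOVA | No | Yes, as outcome | The conditions, not specified |
| Regression, up to six predictors | Not stated | Not stated | Neither |
| Mediation | No | No (mediator is rumination) | ABM and symptom change |
| Moderated mediation | No | No (network is the moderator) | ABM and depressive symptoms |

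The ANOVA is a valid randomised question, but not that of hypothesis 1. No model has network change predicting 6-month symptoms.

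**2. The plan's figure of 34.** For a group-by-time interaction, the noncentrality is f² × N × m / (1 - rho), with k groups, m time points and (k-1)(m-1) and (N-k)(m-1) degrees of freedom. The effect size is read as f = 0.25, with alpha .05 and power .80; k, m and rho are not stated. With k = 2, m = 2 and rho = .5, the noncentrality at N = 34 is 0.0625 × 34 × 2 / 0.5 = 8.5, and power is .807. The figure is reproduced. At the same rho, 2×3, 3×2 and 3×3 layouts (groups × times, equal arms) need 28, 42 and 36. A 2×2 layout needs 66 at rho = 0 and 22 at rho = .7. The figure therefore does not settle which arms and periods are meant.

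**3. Illustration of the misreading.** Inputs:
- Arm size: the plan has "By assuming 15 % drop-out at follow-up, 50 patients in each condition", and 50 × 0.85 = 42.5, taken as 42. That dropout belongs to the BDI-II calculation; no completion rate is given for EMA or the bias tasks.
- Assumed: within-arm correlation r between bias change and network change that ABM did not cause; changers are the half of the active arm with the larger bias change; ABM has no effect on the network.

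Under a bivariate normal model, the two halves differ in large samples by 2r√(2/π) SD. Changers differ from sham by half that, r√(2/π). Share of simulated trials with p < .05 (at least 20,000 replicates):

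| r | Halves differ by (SD) | Changers vs non-changers, active arm | Changers vs sham (SD) | Changers vs sham | Active vs sham, as randomised |
|---|---|---|---|---|---|
| 0 | 0 | 5% | 0 | 5% | 5% |
| .2 | 0.32 | 17% | 0.16 | 9% | 5% |
| .3 | 0.48 | 34% | 0.24 | 14% | 5% |
| .4 | 0.64 | 55% | 0.32 | 22% | 5% |

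**4. Power of the randomised test.** Take 42 per arm and a true difference d = 0.5 SD at follow-up, so √(42/2) = 4.583. Baseline-adjusted noncentrality is d × 4.583 / √(1 - rho²); for change scores it is d × 4.583 / √(2(1 - rho)).

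| Pre-post correlation (assumed) | Adjusted | Change score |
|---|---|---|
| 0 | 2.29, 62% | 1.62, 36% |
| .3 | 2.40, 66% | 1.94, 48% |
| .5 | 2.65, 74% | 2.29, 62% |

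The plan's 34 looks easier to reach because, in the 2×2 layout at rho = .5, f = 0.25 means a difference in change of 4 × 0.25 = 1.0 SD.

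**The case against.** The strongest reply is that the randomised comparison is already planned. A reader might infer from Section 3 that no randomised test of network change exists; the Statistical power text contradicts that. What remains is that this comparison is not stated as a hypothesis, leaves its arms and periods open, and does not address the group in hypothesis 1.

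Second, the plan never proposes to split patients by bias change or to analyse the active arm alone. Bias change could equally enter as a continuous predictor across arms, and the reference to ABM in hypothesis 1 can be read as purely temporal. This stands. A reader might take the 17-55% as an inflated error rate in a planned test. It is not: for r above 0 it is the chance of finding a real correlation that could then be misattributed, under a split chosen for illustration. Against sham, the same assumptions give 9-22%.

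Third, the six-predictor regression may have been meant for hypothesis 2. Its 81 is reproduced as a two-sided test of one coefficient among six predictors at f² = 0.10, which would suit that use. Nothing in the text links the two, however, and a regression alone would not justify the causal verb. Because part of the document and its figures are missing from the available text, absence can be claimed only for that text.

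Fourth, a hypothesis may be causal. That is fair: the limit belongs on how results are reported.

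**Conclusion.** The point holds as a mismatch between hypotheses and analyses that should be settled before outcome data are analysed. Hypothesis 1 concerns a group formed after randomisation, without a comparator; the planned ANOVA does not use that group; hypothesis 2 has no assigned model. The risk is misattribution, and its size depends on an unknown r and on how changers are defined and compared.

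Two stronger conclusions are not supported. The figure of 34 does not show that a two-arm, two-period analysis was intended, since that depends on an assumed correlation. The primary active versus placebo tests are not undermined.

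**What to change.** 1. State the secondary test of an ABM effect on networks as active versus sham in all randomised patients with data. The outcomes are follow-up density and follow-up rumination strength, each adjusted for its own baseline value. Make Section 3 and the Statistical power text agree on arms and EMA periods.
2. Analyse continuous bias change against network change, and network change against 6-month BDI-II, in the active and sham arms together, adjusted for arm and baseline values. Name the bias measure in advance, since the plan has two. The assessment-only arm may be added as a sensitivity analysis. State whether the six-predictor regression serves either analysis. Report both as exploratory associations, not as effects of ABM or of network change.

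No new patients, visits or measures are needed, because baseline and follow-up EMA are already planned. The price is that the mechanistic claims become associations, and that the randomised test has only moderate power: about 62-74% for 0.5 SD and 27-35% for 0.3 SD, with 42 per arm and assumed pre-post correlations of 0 to .5. Baseline adjustment still does better than comparing change scores, which gives 36-62% for 0.5 SD.

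### BDI-II power is stated for an assumed responder contrast, while the planned analysis is of symptom change without stated baseline adjustment; that power does not extend to a 3-point mean difference

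*Combined protocol and SAP*

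**What the plan says.** The Statistical power paragraph in section 4.1 bases the ABM effect on "an assumption that 20 % in the placebo group will report 3 points improvement on BDI-II at follow-up compared to 50" % under active ABM. The rates are labelled an assumption and no source is given. With 15% loss, 80% power and alpha .05, it arrives at 50 patients per condition, 100 for the two arms compared.

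The same paragraph cites a national guideline that "suggests a difference of ≥ 3 BDI-II points is a clinically significant treatment effect for depression".

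Section 3 states the outcome as symptom reduction: "Active vs placebo ABM will decrease depressive symptoms (6 months) and this effect will be mediated by the change in state rumination". The Mediation and moderation analysis paragraph plans a Baron and Kenny analysis "investigating whether the relation between ABM and symptoms change is mediated by rumination". That procedure contains a regression of symptom change on ABM (the total-effect step). The text names no covariate for it and plans no responder comparison. No BDI-II standard deviation, expected mean difference or baseline-to-outcome correlation is given.

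**The concern.** Three points appears in two roles. In the power assumption it is the improvement an individual must show to be counted. In the guideline sentence it is a difference attributable to treatment. Power for the first does not automatically apply to the second, yet the two sit side by side and a reader may take the 80% as covering both.

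What is at stake is how a null BDI-II result would be read against the 3-point criterion. There is also precision to gain: baseline BDI-II is needed anyway to compute change, and using it as a covariate normally narrows the interval at no cost in patients.

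**Working it through.** **Inputs from the plan.** 20% and 50% improvers; alpha .05 (two-sided assumed, as sidedness is not stated); power .80; 15% loss; 50 per arm. Completers: 50 × 0.85 = 42.5, taken as 42 per arm.

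**Assumed inputs.** SD of BDI-II change 4 to 10 points; baseline-to-outcome correlation r of 0.3 to 0.7. The documents give neither.

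**1. The plan's own figure.** For two proportions with pooled variance, n per arm = [1.96√(2 × 0.35 × 0.65) + 0.8416√(0.2 × 0.8 + 0.5 × 0.5)]² / 0.30² = 38.5, so 39. Allowing for loss, 39/0.85 = 46. Fisher's exact test needs 44 per arm, and 44/0.85 = 52. The stated 50 lies between. At 42 completers per arm the pooled z test has 84% power (exact binomial enumeration). Fisher's test has 78% at 42 and 80% at 43. The sample size is sound for the contrast stated.

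**2. That contrast on a continuous scale.** If change is normal with equal SDs, 50% versus 20% beyond a fixed cut is a shift of z(0.5) − z(0.2) = 0.84 SD. A t test of that shift with 42 per arm has about 97% power. In points the shift is 5.0 at SD 6, 6.7 at SD 8 and 8.4 at SD 10. It equals 3 points only at SD 3/0.8416 = 3.6.

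**3. Power for a 3-point mean difference.** Noncentral t, 42 per arm, d = 3/SD, 82 degrees of freedom. With baseline adjustment, the residual SD is SD of change × √((1 + r)/2), with 81 degrees of freedom. This form assumes equal baseline and follow-up variances.

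| SD of change | 4 | 5 | 6 | 8 | 10 |
|---|---|---|---|---|---|
| Unadjusted | 92% | 78% | 62% | 40% | 27% |
| Adjusted, r = 0.3 | 99% | 92% | 80% | 56% | 39% |
| Adjusted, r = 0.5 | 98% | 88% | 74% | 50% | 35% |
| Adjusted, r = 0.7 | 96% | 84% | 69% | 45% | 31% |

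The difference detectable with 80% power is 0.62 SD of change unadjusted, and 0.50 / 0.54 / 0.57 SD adjusted at r = 0.3 / 0.5 / 0.7. Three points is therefore detectable if the SD of change is at most 3/0.619 = 4.85 unadjusted, or 6.0 / 5.6 / 5.3 adjusted.

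**4. Reading a null result.** The unadjusted 95% half-width is 1.989 × SD × √(2/42) = 0.434 × SD. An estimate of zero excludes 3 points only if the SD of change is below 3/0.434 = 6.9. With adjustment and equal variances, the limit is 8.6 / 8.0 / 7.5 at r = 0.3 / 0.5 / 0.7.

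**5. Gain from adjustment.** Let k be the ratio of follow-up SD to baseline SD. The ratio of adjusted to change-score variance is k²(1 − r²)/(1 + k² − 2rk). At k = 1 this is (1 + r)/2, a reduction of 35 / 25 / 15% at r = 0.3 / 0.5 / 0.7. At k = 1.15 the reduction is about 26 / 15 / 5%, and at k = 1.3 about 19 / 9 / 1%.

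**The case against.** The strongest reply is that nothing is shown to be underpowered. The sample size is right for its stated basis, and a continuous test under the same assumption does better. The plan nowhere claims 80% power for a 3-point mean difference. All of that stands. A reader might infer that the trial is too small for BDI-II, but without an SD the documents do not support this: across the assumed grid, power runs from 27% to 99%. A reader might also infer that the stated power is uninformative about the planned analysis. That goes too far, since it does inform power for a 0.84 SD shift. What does not follow is power for a smaller effect.

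Second, the Statistical power paragraph also sizes a regression: "Given multiple regression analysis with up to six predictors and a small effect size", n = 81. This reproduces as a test of one coefficient at f² = .10 with six predictors (power .802). For a 1:1 treatment term, f² = d²/4, so d = 2√0.10 = 0.63 residual SD. It may be meant for the symptom model, and baseline BDI-II may be among the six predictors. But neither outcome, tested term nor predictors are named, so it does not settle the matter.

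Third, a responder analysis could be prespecified instead. That would align the power with the test, but it would still not address the 3-point treatment difference.

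A reader might finally suspect that the power calculation refers to a visit before 6 months, because the EMA paragraph lists "three separate two-weeks of EMA (baseline, follow-up and six months" separately. The design paragraph describes a "randomized controlled, double blind clinical trial with 6 months follow-up", and the schedule figure is not available here, so no conflict is established.

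**Conclusion.** The concern holds in a limited form. The power stated for the ABM effect belongs to an assumed, unsourced responder contrast, while the planned outcome is symptom change with no stated baseline adjustment. Fifty per arm is adequate for that contrast and conservative for a continuous test of the same shift. It gives 80% power for a 3-point mean difference only if the SD of change is about 4.85 points or less unadjusted. This limit assumes 42 completers per arm, a two-sided 5% test and equal SDs.

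The available improvement is baseline adjustment. A reader might take the 35 / 25 / 15% variance reduction as general. It is not: it requires equal baseline and follow-up variances and shrinks when follow-up variance is larger, to 19 / 9 / 1% at an SD ratio of 1.3. The missing source for the two rates and the unlabelled n = 81 regression are gaps in detail, not errors. This should be fixed; confidence is medium because no SD or correlation is given.

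**What to change.** Specify the active-versus-sham total-effect step as a continuous BDI-II comparison at 6 months, by ANCOVA or a mixed model with baseline BDI-II as covariate. Report the mean difference and 95% CI against 3 points, and treat any responder rate as descriptive.

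State power for that analysis as the detectable difference at 42 completers per arm: about 0.62 SD of change unadjusted and smaller with adjustment (about 0.54 SD at r = 0.5 with equal variances). Convert it to points over a stated, assumed SD range; unadjusted, 0.619 × SD gives about 3.1, 3.7, 4.9 and 6.2 points at SD 5, 6, 8 and 10. Keep 20% versus 50% as a labelled planning assumption, with its source if there is one, and say which outcome and term the n = 81 regression covers.

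The cost is rewording two paragraphs, with no extra patients, visits or data. The downside is that the stated power may look less favourable, and the size of the gain from adjustment is unknown in advance.
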